#### **Project Description:**

The global prevalence of knee osteoarthritis (OA) is estimated at greater than 250 million persons or 3.6% of the world population, ranking  $23^{rd}$  on the list of the most common sequelae. Knee OA is the most prevalent cause of mobility dependency and disability, with the time spent living with symptoms averaging 26 years. More than two-thirds of Americans age  $\geq 20$  years are overweight or obese. Two in three people who are obese will develop symptomatic knee OA in their lifetime. In addition to the strong relationship between obesity and knee OA, a recent systematic review found no healthy consequences of overweight/obesity, even in individuals who are metabolically healthy.

In 2004 we reported that a 5% weight loss, when combined with exercise, resulted in a 30% decrease in pain and a 24% improvement in function. Our recently completed trial entitled Intensive Diet and Exercise for Arthritis (IDEA) sought to improve on our work with a more intensive weight loss intervention, 2 to 3 times the weight loss we had recently achieved. IDEA compared intensive diet (D) and exercise (E) interventions, separately and in combination, across an 18-month intervention period in 454 overweight and obese older adults with radiographic knee OA. An intent-to-treat analysis revealed that after 18 months the D+E group reduced pain by 51% compared to 25% and 28% for the D only and E only groups, respectively. The D+E group was also superior to the E group on self-reported physical function, health related quality of life, and walking speed, and had significantly lower knee joint loading and serum levels of IL-6, a pro-inflammatory cytokine. On average, our D+E intervention was twice as effective at

relieving pain as previous long-term OA trials. We concluded that wider adoption of intensive weight loss with a goal of at least 10% of baseline body weight combined with exercise could reduce the burden of disability related to knee OA.

IDEA was an efficacy study with impressive results, a trial designed to determine the effects of intensive diet and exercise *under ideal circumstances*. However, a common concern from physicians who treat people with knee OA is lack of practical means to implement this treatment in the clinical environment. Indeed, there is no evidence regarding how this efficacious intervention could be successfully adapted to be effective in real world clinical and community settings and also be cost effective.

We plan to conduct the first long-term (18 months) pragmatic (i.e., effectiveness) trial of intensive diet and exercise in older adults with knee OA under more usual conditions in both rural and urban communities across North Carolina. Participants (age  $\geq$  50 years; BMI  $\geq$  27 kg/m^2) will be randomized to one of 2 groups: diet-induced weight loss and exercise or an attention control group. The sample will consist of 820 ambulatory, community-dwelling persons that meet the ACR clinical criteria for knee osteoarthritis. The primary aim is to compare the intervention effects on knee pain. Secondary aims will compare the intervention effects on self-reported function, mobility, health related quality of life, and the cost effectiveness and budgetary impact of the intervention.

This program will deliver state-of-the-art weight-management techniques using procedures that are new to this area of research in a community setting. Our proposed study is innovative in at least 6 important ways.

- 1. The first long-term trial of diet-induced weight loss and exercise in adults with knee OA delivered in a practical, less rigorously monitored, community setting. We will design and implement this intervention to make it cost-effective and to serve as a blueprint for diverse communities nationwide. If successful, the results can inform healthcare payers about the first non-pharmacologic treatment of proven benefit for overweight and obese adults with knee OA that also promises to decrease medical care costs.
- 2. The first pragmatic behavioral health trial targeting rural and urban sites. Few pragmatic trials have focused on rural populations (Fortney et al; Gooch et al; Schmidt et al), and none was designed to affect behavior change using community health interventionists. About 25% of the US population lives in diverse rural communities. Most have fewer services and resources than urban communities (US Dept. of Agr). They report poorer health-related quality of life (National Rural Health Assoc.), reflecting higher prevalence of many disorders, including OA. Tailoring a non-pharmacologic intervention for communities with limited healthcare access would be a breakthrough for public health (National Rural Health Assoc.).
- 3. The first evidence that this non-pharmacologic intervention can be implemented costeffectively in US communities. Successful results will lead to step-by-step guidelines regarding the selection of community intervention sites, ways to engage the medical community, and how to deliver a weight-loss and exercise intervention. In addition to the well-established association between obesity and knee OA, strong relationships exist

between high BMI/obesity and coronary heart disease, type 2 diabetes, high blood pressure, stroke, dyslipidemia, and certain types of cancer (Bhaskaran et al; Campbell ). This trial will provide a model for community leaders to develop and execute an effective diet and exercise program at a reasonable cost that will engage local physicians and healthcare providers who treat knee OA, obesity, and related comorbidities.

- 4. A practical treatment option for physicians who treat the comorbidities associated with high BMI. Both the CDC and the American Cancer Society have strategic initiatives that encourage community-based interventions to effectively reduce overweight and obesity (Bauer et al; Campbell).
- **5.** *Focus on implementation and scalability of treatment approaches.* The innovative features of the proposed study will bridge short-term efficacy and long-term outcomes. Identifying and applying the factors critical for intervention sustainability ensure translation from research to practice.
- 6. *Formal assessment of cost-effectiveness and Budget Impact Analysis*. Although rarely performed in pragmatic trials, we will formally assess the cost-effectiveness of the implemented strategies. Results will allow clinicians and policymakers to assess the feasibility of community-based implementation

The proposed study is uniquely designed to identify a practical, effective, non-pharmacologic therapy capable of reducing knee pain and improving function and quality of life in rural and urban communities of older, overweight and obese adults with knee OA.

# **Primary Hypothesis and Aim**

**Hypothesis 1**. A pragmatic, community-based, diet-induced weight-loss and exercise intervention will significantly reduce knee pain among overweight and obese adults aged  $\geq 50$  years with knee OA compared to an attention-control group.

Aim 1. To determine whether a pragmatic, community-based, 18-month diet-induced weightloss and exercise intervention implemented in three North Carolina counties with diverse residential (from urban to rural) and socioeconomic composition significantly decreases knee pain [as measured by the Western Ontario McMasters Universities Osteoarthritis Index (WOMAC) pain subscale] in overweight and obese adults with knee OA compared to an attention-control group.

## Secondary Hypotheses and Aims

**Hypothesis 2**. A pragmatic, community-based, diet-induced weight-loss and exercise intervention will significantly improve self-reported function, health-related quality of life, and mobility among overweight and obese adults aged  $\geq 50$  years with knee OA compared to an attention-control group.

**Aim 2.** To determine whether a pragmatic, community-based, 18-month, diet-induced weightloss and exercise intervention improves WOMAC self-reported function, health-related quality of life as measured by the physical subscale of the SF-36 questionnaire and 6-minute walk

distance (an accepted measure of mobility) in overweight and obese adults with knee OA compared to an attention control group.

**Hypothesis 3.** A pragmatic, community-based, diet-induced weight-loss and exercise intervention will be a cost-effective addition to treatment modalities in overweight and obese persons with knee OA.

**Aim 3.** To establish the cost-effectiveness of this pragmatic, community-based, multimodal dietinduced weight-loss and exercise program by conducting cost-effectiveness and budgetary impact analyses using data from the current trial in a validated computer-simulated model of knee OA.

## Study Design

We will randomize 820 overweight and obese (BMI  $27 \ge kg/m^2$ ), adults age  $\ge 50$  yrs knee OA into one of 2 groups: an intensive dietary restriction-plus-exercise (D+E) group or an attention control (nutrition and health) group. Persons who have begun screening once we hit our overall recruitment goal of 820 will be allowed to complete the screening process therefore up to 840 persons may be enrolled into the study. Forsyth, Johnston, and Haywood Counties' recruitment goals are 420, 210, and 210, (total 840) respectively. Our minimum weight-loss goal for the weight-loss group will be 10% of body weight. The exercise intervention will meet 3 days/wk at the clinical site. The intervention will be comprised of both aerobic and strength training exercises. When participants are unable to come into the facility for intervention, sessions will be conducted via phone or through video conferencing. The nutrition and health group will meet 5 times over an 18 month period and receive a combination of webinars, video messages, text messages, emails (via personal email or Facebook), phone calls, and mailings for the remaining months. Participants will be allowed to choose their preferred method.

## Primary Endpoint

Western Ontario McMasters Universities Osteoarthritis Index (WOMAC). We will measure self-reported physical function and pain using the WOMAC (scores will be pulled from the KOOS Questionnaire in which the WOMAC is embedded). The LK version asks participants to indicate on a scale from 0 (none) to 4 (extreme) the degree of difficulty experienced in the last week due to knee OA. Individual scores for the 17 items are totaled to generate a summary score that could range from 0-68, with higher scores indicating poorer function. The pain index assesses participants' pain on the same scale, ranging from 0 (none) to 4 (extreme). The pain subscale consists of 5 items and total scores can range from 0-20, with larger scores indicating greater dysfunction. This instrument has been validated and recommended by the Osteoarthritis Research Society as the health status measure of choice in older adults with knee OA. In order to measure the minimal clinically improvement difference (MCID) participants will be asked to compare their knee pain to how it was at the beginning of the study.

## Secondary Endpoint

Mobility. Our primary mobility measure will be 6-minute walk distance. Participants are told to walk as far as possible in 6 minutes on an established course. No personal timing devices are permitted, and participants are not provided feedback during the test. Results are significantly correlated to treadmill time and symptom-limited maximal oxygen consumption (r = 0.52 and r

= 0.53, respectively) and have a 3-month test-retest reliability of 0.86 (Pennix et al). The Short Physical Performance Battery (SPPB) will also be used to measure mobility (Guralnik et al). The SPPB is comprised of the following tests (balance, walking speed, and chair rise). A test of ascending and descending stair activity measured by the time (in seconds) it takes to ascend and descend a flight of 8 steps with 20cm (8 inch) step height and handrail will also be performed.

Cost Effectiveness Resource utilization will be collected by questionnaire, with domains including visits to clinicians (physicians, nurses, physical therapists, others), tests, medications, injections, surgery, alternative therapies. The Work Productivity and Activity Impairment index (WPAI) will be used to assess absenteeism and reduced productivity while at work (presenteeism).

Body weight, height, hip/waist circumference, BMI. Body weight and height will be obtained using standard techniques. Only persons with a BMI  $\ge 27$  kg/m^2 will be eligible. Circumference measurements will be collected using standard techniques.

[figure not shown]
Medical History, Medications, and Blood Pressure. Participants will be given forms to assess medical history and presence of comorbidities. Participants will also be asked questions about their medical history during the phone screen so as to reduce participant burden by identifying potential exclusion criteria. Participants will be administered a medication questionnaire adapted from the ARIC study and widely used in field research and in our prior studies at each testing visit (ARIC).

It is designed to obtain information about all prescription and over-the-counter medicines and supplements used during the 2 weeks prior to the interview (home or clinic). The participants will be mailed the medication form to fill out at home and will return the form to the interviewer. Participants may also be asked to provide the interviewer with all medicine containers so that the interviewer can transcribe the information. In addition participants will be encouraged to notify the study staff of any medication changes during the course of the study.

In addition to the medical history and medication questionnaires, participants will also be given a risk stratification questionnaire at the first screening visit. The purpose of this questionnaire is to determine if participants will need medical clearance prior to enrolling into an exercise program. The determination is based on the presence/absence of cardiovascular/pulmonary/metabolic disease risk factors, sign and symptoms, and known medical history. The following schematic demonstrates how medical clearance will be determined (Figure 1). The American College of Sports Medicine recommends that all patients are first screened to determine if they are participate in regular exercise (defined as performing planned, structured physical activity at least 30 min at moderate intensity on at least 3 days per week for at least the last 3 months). If the participant responds with no medical clearance will be not be needed for those who have not been diagnosed with any CV, Metabolic, or renal disease and are showing no signs/symptoms. If the response is yes those who have not been diagnosed as well as those with a diagnosis and are asymptomatic will not need physician clearance (Riebe et al., 2015). Like the previous recommendations this is only for moderate intensity exercise. Our exercise protocol falls within

this moderate intensity range. The original protocol called for participants to exercise in the range of 50-75% of their maximal heart rate reserve (i.e., moderate to high intensity). The range was previously modified to 40-60% of maximal heart rate reserve (i.e., moderate intensity). Hence, participants that have no diagnosis of CV, Metabolic, or renal disease or those that have been diagnosed but are asymptomatic will be enrolled without the need for physician clearance. *Those who have signs and symptoms or who have been diagnosed but do not meet the exercise criteria will require medical clearance from their physician*. Final approval and acceptance into the program for patients will be provided by our study physician. It's worth noting the risk of serious adverse events occurring during properly supervised exercise is extremely low (< 1 per 100,000 hours of exercise) even in older adults, with cardiovascular disease. Blood pressure will also be measured.

Figure 1: Exercise preparticipation health screening logic model for aerobic exercise participation (Updating ACSM's Recommendations for Exercise Preparticipation Health Screening, MSSE 2015)

Measures of Quality of Life and Self-Efficacy. The SF-36 is the most widely used and carefully validated measure of health related quality of life and will be used to yield 2 broad summary scores: physical health and mental health (Ware and Sherbourne). The Eurqol Quality of Life will also be used to measure quality of life and health state (Brooks; EuroQuol). The walking efficacy for duration scale measures one's ability to walk/jog at a moderately fast pace for various durations (McAuly and Mihalko). The Positive and Negative Affect (PANAS) measures

both positive and negative affect, leading to more insightful outlooks regarding participants' feeling states. This scale consists of 20 items that reflect the intensity of how the participant "feels" right now (Watson et al). The gait efficacy/environmental efficacy scale will ask the participants' confidence in performing certain activities (McAuley et al.). Among the various components of subjective well-being, the Satisfaction with life scale is focused to assess global life satisfaction (Diener et al). The Weight Efficacy Lifestyle Questionnaire (WEL) is a 20-item measure employed to assess self-efficacy for weight management (Clark et al). The Perceived Stress Scale (PSS) will measure the degree to which people perceive their lives as stressful (Cohen et al). The adherence self-efficacy questionnaire is designed to assess beliefs in one's ability (confidence) to continue exercising at various intensities and frequencies (McAuly and Mihalko).

Pain Catastrophizing Scale (PCS). The PCS questionnaire will be used to assess catastrophizing (rumination, magnification, and helplessness) (Sullivan et al).

Knee injury and Osteoarthritis Outcome Score (KOOS). The KOOS questionnaire will be used to assess the patient's opinion about their knee and associated problems. The KOOS evaluates both short-term and long-term consequences of knee injury and also consequences of primary osteoarthritis (OA) (Roos & Lohmander).

Intermittent and Constant Osteoarthritis Pain (ICOAP). The ICOAP assesses pain in individuals with knee osteoarthritis taking into account both constant and intermittent pain experiences (Hawker et al).

Dietary Intake. National Cancer Institute Modified Health Habits and History Questionnaire (HHHQ) provides nutrient assessment of dietary intake.

Health Literacy. Behavioral Risk Factor Surveillance System measures health literacy.

Physical Activity. The Physical Activity Scale for the Elderly (PASE) has proven reliable in many of our clinical trials, including a group of 254 men and women aged  $\geq$ 65 yrs (Washburn et al).

Cognitive Functioning/Depression. The MOCA will be used to measure cognitive function (Nasreddine et al). Depression will be measured using the Center for Epidemiologic Studies Depression Scale (Burnam et al).

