# Exclusion Criteria:

- 1. Significant co-morbid disease that would threaten safety or impair ability to participate in interventions or testing (Method: Medical history; medications; physical exam; telephone pre-screen; risk stratification)
  - a. Blindness
  - b. Type 1 diabetes
  - c. History or symptoms of coronary artery disease or pulmonary disease with no medical clearance (symptoms include angina, unreasonable breathlessness, dizziness/fainting/blackouts)
  - d. Unable to walk without a device
  - e. Lower extremity fracture (within previous 3 months)
  - f. Joint Replacement (excluded if double KR or within previous 6 months)
  - g. Knee injection or surgery (within previous 3 months)
  - h. Lower extremity injury that affects activities of daily living
  - i. Bariatric Surgery
- 2. Not sufficiently overweight or obese,  $BMI < 27 \text{ kg/m}^2$  (Method: Ht/Wt)
- 3. Not having knee pain: (Method: <1 on the pain scale, WOMAC and Telephone Screen)
- 4. Inability to finish 18-month study or unlikely to be compliant (Method: Telephone Screen, Screening Interviews)
  - a. Planning to leave area > 2 month during the next 18 months
  - b. Unwilling to change eating or physical activity habits
  - c. Unwilling to attend exercise/diet sessions
  - d. Participating in another intervention study (only if the other study has requested they not be enrolled)
  - e. Living > 30 minutes from the intervention site
- 5. Age, age < 50 (Method: Telephone Screen & Demographics Forms)
- 6. Other conditions that may prohibit the effective delivery of the intervention (Method: Telephone Screen)
  - a. Unable to provide own transportation to exercise center
  - b. Unable to read or write, cannot speak or read English

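### The clearance waiver for diagnosed but asymptomatic participants omits the regular-exercise condition and contradicts the sentence that follows it

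*Combined protocol and SAP*

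**What the plan says.** All of this is in the Medical History, Medications, and Blood Pressure text under Secondary Endpoint.

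- **Background scheme.** The protocol summarises an exercise-screening recommendation that first asks whether a person already exercises regularly: at least 30 minutes at moderate intensity, on at least 3 days a week, for at least the last 3 months. If the answer is no, clearance will "not be needed for those who have not been diagnosed with any CV, Metabolic, or renal disease and are showing no signs/symptoms". If it is yes, the waiver is wider: besides the undiagnosed, "those with a diagnosis and are asymptomatic will not need physician clearance". The protocol adds a limit on intensity: "Like the previous recommendations this is only for moderate intensity exercise".
- **The study's waiver.** After noting that the exercise range was lowered from 50-75% to 40-60% of heart rate reserve, a sentence opening with Hence exempts people without a diagnosis and states that "those that have been diagnosed but are asymptomatic will be enrolled without the need for physician clearance".
- **The study's requirement.** The next sentence, in italics, requires clearance for people with signs and symptoms, and for those "who have been diagnosed but do not meet the exercise criteria will require medical clearance from their physician".
- **Backstop.** The paragraph continues: "Final approval and acceptance into the program for patients will be provided by our study physician".

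**The concern.** The background scheme exempts diagnosed, asymptomatic people only if they already exercise regularly. The waiver sentence keeps the exemption and drops the condition. The sentence after it puts the condition back, but as a requirement and not as an exception to the waiver. Staff screening a diagnosed, asymptomatic person who does not exercise regularly can cite the protocol for either decision.

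This is the stated medical screen before an 18-month exercise programme for adults aged 50 or over with a BMI of at least 27. No eligibility criterion requires prior regular exercise, so the affected profile can enter the trial. What is at stake is safety screening and its consistency across three counties, not the statistical analysis.

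**Working it through.** No figure in the plan is at issue, so the check is one of logic. Three yes/no facts decide the matter: regular exerciser, diagnosis (cardiovascular, metabolic or renal), and signs or symptoms. They give 2 × 2 × 2 = 8 profiles.

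Each of the two sentences can be parsed in two ways:

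- **W1**: in the waiver, asymptomatic qualifies only the diagnosed group. Waived if not diagnosed, or if without symptoms.
- **W2**: asymptomatic qualifies both groups. Waived if without symptoms.
- **R1**: in the requirement, the exercise criteria qualify only the diagnosed group. Clearance if symptomatic, or if diagnosed and not exercising.
- **R2**: the exercise criteria qualify both groups. Clearance if symptomatic or diagnosed, and not exercising.

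The exercise criteria are not defined in that sentence. The regular-exercise definition earlier in the same text is the only candidate.

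| Exerciser | Diagnosis | Symptoms | W1 waives | W2 waives | R1 requires | R2 requires | Proposed waiver |
|---|---|---|---|---|---|---|---|
| no | no | no | yes | yes | – | – | yes |
| no | no | yes | yes | – | yes | yes | – |
| **no** | **yes** | **no** | **yes** | **yes** | **yes** | **yes** | **–** |
| no | yes | yes | – | – | yes | yes | – |
| yes | no | no | yes | yes | – | – | yes |
| yes | no | yes | yes | – | yes | – | – |
| yes | yes | no | yes | yes | – | – | yes |
| yes | yes | yes | – | – | yes | – | – |
| **Total** | | | 6 | 4 | 5 | 3 | 3 |

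A conflict is a profile both waived and required; a gap is a profile that is neither.

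| Waiver | Requirement | Conflicts | Gaps |
|---|---|---|---|
| W1 | R1 | 3 | 0 |
| W1 | R2 | 2 | 1 |
| W2 | R1 | 1 | 0 |
| W2 | R2 | 1 | 2 |
| Proposed | R1 | 0 | 0 |
| Proposed | R2 | 0 | 2 |

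The bold profile conflicts in all four pairings of the current sentences. The extra conflicts under W1 concern undiagnosed people with symptoms. They depend on how the waiver is parsed, and the conclusion does not rest on them.

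**Which sentence is wrong?** For someone who does not exercise regularly, the background scheme waives clearance only when there is neither a diagnosis nor any symptom. It therefore agrees with the requirement, and the waiver is the outlier.

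**Does the lower intensity justify the wider waiver?** No. The whole two-branch scheme is already limited to moderate exercise. Moderate intensity is the condition for using the scheme, so it cannot also be a reason to drop one of its branches.

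**The case against.** The best defence is that a general statement followed at once by a more specific one is normally read as rule and exception. On that reading the conflict disappears, and staff who read the whole paragraph have one workable rule. As a guide to intent this stands. As a defence of the wording it does not: no word such as except or provided links the two sentences, and the waiver is categorical and framed as the conclusion.

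Figure 1, named as showing how clearance is decided, and the risk stratification questionnaire may both apply the right rule. Neither can be seen here, so an effect on actual screening cannot be shown. Even a correct figure would leave the two sentences opposed.

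Other safeguards also narrow the exposure:

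- Exclusion 1 bars "Significant co-morbid disease that would threaten safety or impair ability to participate in interventions or testing", and 1b removes type 1 diabetes.
- Exclusion 1c bars people with a history or symptoms of coronary or pulmonary disease who lack medical clearance. It does not reach type 2 diabetes, renal disease or non-coronary cardiovascular disease. For an asymptomatic person with a coronary history, 1c itself conflicts with the waiver.
- Final approval by the study physician limits risk, but it is not clearance from the participant's own physician, which is what the requirement asks for.
- The protocol's very low event rate (below 1 per 100,000 hours) is for properly supervised exercise. The Interventions section makes only two of the three weekly sessions center based, although Study Design places all three at the clinical site. The emergency equipment is at the sites.

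These points support calling this a wording error and not a faulty design. They do not make the two sentences agree.

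**Conclusion.** The concern holds. As written, one of the eight profiles (diagnosed, asymptomatic, not exercising regularly) receives opposite instructions from two adjacent sentences under every literal reading tested. The intended rule can be recovered from the second sentence and the background scheme, and several safeguards reduce the practical risk. It is still a safety-screening rule that contradicts itself, and it should be corrected.

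The conclusion assumes that the exercise criteria mean the regular-exercise definition in the same text, and that the second sentence is not silently an exception to the first. The number of participants affected cannot be estimated from the documents, and none is claimed. Sample size, power and the primary analysis do not change.

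**What to change.** Reword the waiver along these lines:

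> Hence, clearance from the participant's own physician is waived for (a) people who have no CV, metabolic or renal diagnosis and no signs or symptoms, and (b) people with such a diagnosis who are free of symptoms and already meet the regular-exercise definition. Exclusion 1c still applies.

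Keep the requirement sentence, and state in it that people with signs and symptoms need clearance regardless of exercise habits. That closes the two gaps left under R2 (symptomatic regular exercisers, with or without a diagnosis), so no conflict and no gap remains under either reading. The no-symptoms condition for undiagnosed regular exercisers comes from the requirement sentence; the background scheme does not state it for them. The reminder about 1c is needed because the eight-profile check does not model that exclusion.

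Then confirm that Figure 1 and the risk stratification questionnaire apply the same rule. If the sponsor in fact meant the broad waiver, the requirement sentence and the account of the scheme would have to change instead, with a reason given.

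The cost is a small text change and a check of two documents, with no extra study visits. Some diagnosed people who do not exercise regularly will need their physician's clearance, which the requirement sentence already demands.
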